6.11.7.2. Echocardiography

Normal/Abnormal results of echocardiography will be listed.

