Investigational Product, Dosage, and Mode of Administration or Intervention:**Part A**

- Cohort 1: 15 mg/kg of olaratumab on Day 1 and Day 8, and 25 mg/m² of doxorubicin on Day 1, Day 2, and Day 3 of every 21-day cycle.
- Cohort 2: 15 mg/kg of olaratumab on Day 1 and Day 8, and 75 mg/m² of doxorubicin on Day 1 of every 21-day cycle.
- Cohort 3: 20 mg/kg loading dose of olaratumab on Day 1 and Day 8 in Cycle 1, followed by 15 mg/kg on Day 1 and Day 8 in subsequent cycles, and 75 mg/m² of doxorubicin on Day 1 of every 21-day-cycle.

Part B

This part consists of 1 dose level: 15 mg/kg of olaratumab on Day 1 and Day 8 of every 21-day cycle.

Planned Duration of Treatment:

Patients will be on treatment until one of the discontinuation criteria is met.

Treatment period: 21 days/cycle

Follow-up Period: 28 days

Criteria for Evaluation:

Safety: Dose-limiting toxicities, treatment-emergent adverse events (TEAEs) using Common Terminology Criteria for Adverse Events (CTCAE) version 4.03 and the Medical Dictionary for Regulatory Activities (MedDRA), laboratory evaluations, vital signs, electrocardiograms and cardiac function as measured by echocardiogram.

Bioanalytical: Serum concentrations of olaratumab (Part A and B) and plasma concentrations of doxorubicin (Part A).

Pharmacokinetics: The primary parameters for analysis will be maximum observed concentration (C_{max}) and area under the concentration-time curve (AUC) from time 0 to the last time point with a measurable concentration, and AUC from time 0 to infinity of olaratumab and doxorubicin. Other noncompartmental parameters, such as half-life, clearance, and volume of distribution, may be reported.

Efficacy: Antitumor activity according to Response Evaluation Criteria in Solid Tumors version 1.1.

Biomarkers: Biomarkers related to the mechanism of olaratumab, the PDGF signaling pathway, and the pathobiology of cancer.

Statistical Methods:

Safety: Dose-limiting toxicities will be listed and summarized by frequency. Adverse events (AEs), including TEAEs, will be listed and summarized in frequency tables using MedDRA. Severity of AEs will be classified using CTCAE version 4.03. Other safety data, such as laboratory tests, echocardiography, and vital signs, will be listed and summarized, if appropriate.

Efficacy: Efficacy data will be listed. Also, efficacy data will be summarized using frequency table or summary statistics, depending on the characteristics of the data.

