A Phase 1b/2 randomized study evaluating the efficacy of doxorubicin with or without olaratumab in the treatment of advanced STS (Study CP15-0806; I5B-IE-JGDG [JGDG]) is currently ongoing. A preplanned efficacy interim analysis has demonstrated prolonged progression-free survival and overall survival when olaratumab (15 mg/kg on Days 1 and 8 of each 21-day cycle) was given with doxorubicin (75 mg/m^2 on Day 1 of each cycle). The toxicity profile of olaratumab combined with doxorubicin was acceptable.

In the olaratumab plus doxorubicin treatment arm, there was a slight increase in known doxorubicin-related toxicities events such as nausea, vomiting, and neutropenia. No difference

in febrile neutropenia or major gastrointestinal toxicities was observed and the overall incidence of life-threatening toxicities was similar between the treatment and control arms. Also, increased cardiotoxicity (14.1% in the olaratumab plus doxorubicin arm vs. 9.2% in the doxorubicin arm) was observed. However, this was in line with what could be expected given the higher median number of cycles of doxorubicin received by patients in the treatment arm.

Finally, the scientific justification of investigating olaratumab combined with doxorubicin in advanced STS is compelling based on the role of PDGFR α in tumor cell survival and proliferation and the evidence of antitumor effects in tumor xenograft models. The recent (Studies JGDC and JGDF) and ongoing (Study JGDG) clinical trials have shown a well-tolerated safety profile in olaratumab monotherapy and in combination with doxorubicin. Furthermore, the preliminarily observed prolongation of progression-free survival and overall survival in Study JGDG provides additional justification to conduct this study (Study I5B-JE-JGDK [JGDK]). Part A of Study JGDK is designed to evaluate the safety and tolerability of olaratumab when administered in combination with doxorubicin to Japanese patients with advanced solid tumors, especially advanced STS. This safety information will allow Japanese patients to participate in the following global Phase 3 study.

The sponsor, monitor, and investigators will perform this study in compliance with the protocol, good clinical practice (GCP) and International Conference on Harmonisation (ICH) guidelines, and applicable regulatory requirements.

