- [8] (Part A only)
 - Have a prestudy echocardiogram with an actual left ventricular ejection fraction (LVEF) $\geq 50\%$, within 21 days prior to first dose of study medication.
- [9] All patients agree to use a reliable method of birth control and to not donate sperm during the study and for at least 3 months following last dose of study drug. Acceptable methods of birth control include vasectomy (pipe cut), tubal ligation, barrier method (eg, condoms or pessary) with spermicide, an intrauterine device which has been in place for at least 3 months before first dose of study drug, or the oral contraceptive pill taken for at least 3 months before first dose of study drug.
- [10] Female patients must either be women not of child-bearing potential due to surgical sterilization (at least 6 weeks postsurgical bilateral oophorectomy with or without hysterectomy or tubal ligation) confirmed by medical history, or menopause.
 - or
 - women of child-bearing potential who test negative for pregnancy within 7 days before the first dose of study drug based on serum or urine pregnancy test and agree not to breast feed during the study and for 3 months following the last dose of the study drug(s)

Menopausal women include women with either

- a. spontaneous amenorrhea for at least 12 months, not induced by a medical condition such as anorexia nervosa, and not taking medications during the amenorrhea that induced the amenorrhea (eg, oral contraceptives, hormones, gonadotropin releasing hormone, antiestrogens, selective estrogen receptor modulators, or chemotherapy).
 - or
- b. spontaneous amenorrhea for 6 to 12 months and a follicle-stimulating hormone level greater than 40 mIU/mL.

- [11] Have an estimated life expectancy of ≥ 3 months in the judgment of the investigator.

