7.2.2.4.3. Cardiovascular

Electrocardiogram changes, arrhythmias, tachycardia, and/or chest pain should be managed based on the specific findings.

Patients will undergo baseline LVEF determination by echocardiogram. This evaluation may be repeated at any time during the study if clinically indicated. If an echocardiogram conducted on study indicates a resting LVEF is <50%, then the echocardiogram should be repeated for monitoring. If there is an absolute decrease in LVEF of >20% from the previous evaluation, or if the actual LVEF decreases to ≤40%, then doxorubicin should be discontinued. Doxorubicin should also be discontinued if the patient develops Grade 3 or 4 left ventricular systolic dysfunction (symptomatic congestive heart failure).

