10.4. Safety Analyses

All safety evaluations will be based on the FAS Population (except a DLT summary). Safety variables listed below will be summarized by part and cohort (and by study visit/time point, if applicable).

- Study drug exposure of olaratumab or doxorubicin: number of cycles, number of infusions, duration of treatment (weeks), cumulative dose (mg/kg or mg/m²), dose intensity (mg/kg/week or mg/m²/week), relative dose intensity (%), treatment delays, treatment omissions, treatment reductions, and treatment interruptions.
- TEAEs: MedDRA will be used for categorizing to System Organ Class and Preferred Term. National Cancer Institute-Common Terminology Criteria for Adverse Events will be used for identifying grade and/or relevant event term. In addition to TEAEs, all AEs, SAEs, study drug-related AEs and SAEs, AEs leading to treatment discontinuation (olaratumab or doxorubicin in Part A and olaratumab in Part B), and AEs leading to treatment delay/omission/reduction/interruption (olaratumab or doxorubicin in Part A and olaratumab in Part B) will be summarized.
- DLT: In Part A, the number of patients who experienced any DLTs during Cycle 1 will be summarized by cohort using the DLT Population.
- Deaths, SAEs, other significant AEs: these findings will be listed by patients.
- PS, physical exams, vital signs, laboratory tests and ECG: actual measurements, as well as categorized values of laboratory tests, vital signs, and ECG parameters, will be summarized by part, cohort, and study visit/time point.

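### The SAP lists echocardiography only as an undefined Normal/Abnormal result, so LVEF decline and the protocol's own LVEF limits cannot be described from the planned outputs

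*SAP*

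**What the plan says.** SAP 6.11.7.2 consists of one sentence: "Normal/Abnormal results of echocardiography will be listed". It gives no definition of abnormal, no LVEF value, no change and no summary by cohort. No other SAP section mentions LVEF in an analysis.

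The protocol treats the echocardiogram as a numeric safety measure:

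- The synopsis (Criteria for Evaluation) includes it among the safety criteria: "laboratory evaluations, vital signs, electrocardiograms and cardiac function as measured by echocardiogram".
- The synopsis (Statistical Methods) says: "Other safety data, such as laboratory tests, echocardiography, and vital signs, will be listed and summarized, if appropriate".
- Section 6.1.1, criterion 8, requires LVEF of at least 50% within 21 days before the first dose (Part A).
- Section 7.2.2.4.3 calls for a repeat scan when LVEF is below 50%. It calls for doxorubicin to be stopped on an "absolute decrease in LVEF of >20% from the previous evaluation", or when LVEF is 40% or lower.
- Attachment 1 schedules scans for Part A at screening, before Cycles 5 and 7, and at follow-up. Section 8.1.3.3 has them done locally.

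Protocol 10.4, which sets out the safety analyses, does not name echocardiography. Its list reads: "PS, physical exams, vital signs, laboratory tests and ECG: actual measurements, as well as categorized values".

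**The concern.** Part A's primary objective is the safety and tolerability of olaratumab with doxorubicin. Protocol 5.1 reports from the earlier randomised study that "increased cardiotoxicity (14.1% in the olaratumab plus doxorubicin arm vs. 9.2% in the doxorubicin arm) was observed". A reader of this study's report would expect to see how LVEF moved over treatment and how many patients reached the limits the protocol itself sets.

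The planned output allows neither. It reduces a continuous measure, with three numeric limits attached, to one flag whose meaning is not stated and which may differ between local readers. The SAP is stricter elsewhere. QTc gets numeric thresholds, changes from baseline, plots and a regression (6.11.7.1). Laboratory results are graded from the numbers alone, without investigator assessment (6.11.5).

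**Working it through.** **1. The protocol's figure for cardiotoxicity.** Protocol 5.4 gives 64 patients on the combination and 65 on doxorubicin alone. Then 9/64 = 14.06% and 6/65 = 9.23%, which match the stated 14.1% and 9.2%.

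**2. The flag against the protocol's rule.** Two assumptions are needed. Abnormal is taken as LVEF below 50%, because the documents do not define it. The absolute fall of more than 20% is read as percentage points. Fall = previous LVEF − current LVEF; the stopping rule is met if fall > 20 or current LVEF ≤ 40.

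| Previous → current LVEF (%) | Fall (points) | Flag | Stopping rule in 7.2.2.4.3 |
|---|---|---|---|
| 72 → 51 | 21 | Normal | met (fall) |
| 65 → 54 | 11 | Normal | not met |
| 52 → 49 | 3 | Abnormal | not met |
| 58 → 41 | 17 | Abnormal | not met |
| 55 → 40 | 15 | Abnormal | met (value) |
| 50 → 38 | 12 | Abnormal | met (value) |

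Both flag values occur with the rule met and with it not met.

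**3. Dependence on the assumed cut.** A local reader might call a 21-point fall abnormal even at 51%, and the first row would then change. The general result would not. The protocol has three separate limits (below 50%, 40% or below, fall above 20%), and one yes/no flag cannot identify which was crossed. Under any definition it also omits the size of the change.

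**4. Whether other outputs fill the gap.**

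- The DLT summary covers Cycle 1 only (Protocol 7.2.1.3), when planned doxorubicin is 75 mg/m² (in Cohort 1, 3 × 25). The scheduled on-study scans come later. At full dose cumulative doxorubicin is 4 × 75 = 300 mg/m² before Cycle 5 and 6 × 75 = 450 mg/m² before Cycle 7. Protocol 5.5 gives a Japanese label maximum of 500 mg/m² because of myocardial risk.
- The adverse event tables (SAP 6.11.3 and 6.11.4) show a cardiac finding only if it was reported as an adverse event. Protocol 8.1.2 asks for measurements to be reported when clinically significant. An asymptomatic decline judged not significant would not appear there.

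**5. What LVEF data from this study could show.** Take 6 patients per cohort and 18 in Part A (three cohorts, Protocol 6.2), with P(at least one) = 1 − (1 − p)^n.

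| n | p | Expected cases | P(at least one) |
|---|---|---|---|
| 6 | 14.06% | 0.84 | 0.597 |
| 6 | 9.23% | 0.55 | 0.441 |
| 18 | 14.06% | 2.53 | 0.935 |
| 18 | 9.23% | 1.66 | 0.825 |

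With no events, the 95% Wilson upper limit is z²/(n + z²) with z² = 3.84: 3.84/9.84 = 39.0% for n = 6, and 3.84/21.84 = 17.6% for n = 18. Separating 14.06% from 9.23% with two-sided α of 5% and 80% power (my assumptions) would need about 691 per arm. No output from this study could test that difference. LVEF results would be descriptive.

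**6. Which change to tabulate.** Section 7.2.2.4.3 measures the fall from the previous evaluation. Values of 70, 58 and 48 fall 70 − 48 = 22 points from baseline, but only 12 and then 10 between evaluations. A table of change from baseline alone would flag a patient who did not meet the protocol's fall criterion.

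**The case against.** The strongest opposing case is that cardiac safety is already covered. Clinically significant findings must be reported as adverse events, and all are graded (Protocol 8.1.2). The SAP summarises treatment-emergent events by class, term and maximum grade, together with serious events, deaths, and events leading to doxorubicin discontinuation (6.11.3, 6.11.4). Sites must also report the circumstances and data behind any discontinuation caused by an adverse event (Protocol 8.1.2). This stands. A reader might infer that cardiotoxicity cannot be assessed at all, and the documents do not support that. What is missing is LVEF change outside adverse event reporting.

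A reader might also infer that LVEF values are discarded. The SAP does not say so: it describes one output, and both documents allow further exploratory analyses (SAP 6.1.2, Protocol 10.1). The sound statement is that no LVEF output is planned.

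Nor is there a plain conflict between the documents. The synopsis commitment is conditional on appropriateness, and Protocol 10.4 omits echocardiography, so the sparse SAP text agrees with 10.4. The gap lies partly in the protocol.

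Finally, the protocol says the excess in the earlier study was in line with the higher number of doxorubicin cycles given (5.1, 5.4). The formal tolerability decision here rests on Cycle 1 DLTs, before the first scheduled on-study scan. Both points stand and limit the weight of the concern. They do not justify an undefined flag: every safety output in this study is descriptive, and in small cohorts the individual values carry most of the information.

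**Conclusion.** The point holds as a reporting gap. From the planned outputs one cannot describe LVEF decline that was not reported as an adverse event, and one cannot tell whether the limits in Protocol 7.2.2.4.3 were met. The Normal and Abnormal labels are also undefined.

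The numerical examples rest on an assumed cut of 50%. The inability of one flag to separate three limits, or to give the size of a change, does not.

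The consequence is moderate. No decision rule in the study depends on this output, and nothing here bears on sample size. No view is taken on whether the protocol's LVEF limits are clinically right. The change is worth making because it is cheap and concerns the primary objective of Part A.

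**What to change.** Rewrite SAP 6.11.7.2 for Part A:

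- State how Normal and Abnormal are assigned, if the flag is kept.
- List LVEF by patient and visit, including unscheduled repeat scans, with change from baseline and change from the previous evaluation.
- Summarise by cohort the baseline value, the worst post-baseline value and the maximum decrease.
- Count patients by cohort with LVEF below 50%, with LVEF of 40% or below, and with an absolute decrease above 20% from the previous evaluation, following the wording of Protocol 7.2.2.4.3.

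Add echocardiography to Protocol 10.4, or otherwise align that section with the synopsis.

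The cost is one listing and one table, with no added visits or patients. The documents do not show whether the CRF captures the numeric LVEF, and this should be confirmed first. If it does not, the cost rises to a CRF change and retrospective entry of the values.

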6.12. Biomarker Analyses

For the FAS population, descriptive statistics for biomarkers obtained from blood samples will be provided by part and cohort. Also, listings of all biomarkers will be prepared.

6.13. Subgroup Analyses

Subgroup analyses are not preplanned, but some subgroup analyses may be conducted, if needed.

6.14. Protocol Deviations

Important protocol deviations will be described in a separate document and the information will be provided by the Clinical Trial Manager to the Statistician in an Excel file. The Statistician will convert the Excel file to a SAS dataset, and store both of them in SAS Drug Development (SDD) for the use of analysis.

A listing of protocol deviations will be provided with the Enrolled population.

6.15. Interim Analyses and Data Monitoring

Interim access to safety data will be performed during the study for safety review.

In this study, preplanned interim analysis will be conducted after completing Cycle 1 and the DLT evaluation in Cohort 2 of Part A. Interim safety analyses will be conducted for the decision of joining future global phase 3 studies. Details of the safety analyses will refer to Section 6.11.

Additional interim analyses may be conducted, if needed.

6.16. Annual Report Analyses

The datasets including the following tables and listings will be generated for the Development Safety Update Report (DSUR) reports based on the resource document ‘Statistical Guidance and Mock Tables for the Development Safety Update Report (DSUR) and Periodic Safety Update Report (PSUR) / Periodic Benefit Risk Evaluation Report (PBRER)’:

- Summary of patients demographics by age and gender
- Summary of patients demographics by racial groups
- Summary of cumulative patient exposure information
- Listing of patients who died
- Listing of patients who discontinued study rugs or study due to AEs

Investigator’s Brochure (IB) related analyses may be conducted at the same time as the DSUR analyses if applicable.

6.17. Clinical Trial Registry Analyses

Additional analyses will be performed for the purpose of fulfilling the Clinical Trial Registry (CTR) requirements.

Analyses provided for the CTR requirements include the following:

Summary of adverse events, provided as a dataset which will be converted to an XML file. Both Serious Adverse Events and ‘Other’ Adverse Events are summarized: by part and cohort, by MedDRA term.

- An adverse event is considered ‘Serious’ whether or not it is a TEAE.
- An adverse event is considered in the ‘Other’ category if it is both a TEAE and is not serious. For each Serious AE and ‘Other’ AE, for each term, part and cohort, the following are provided:
 - the number of participants at risk of an event
 - the number of participants who experienced each event term
 - the number of events experienced.
- Consistent with www.ClinicalTrials.gov requirements, ‘Other’ AEs that occur in fewer than 5% of patients in every part and cohort may not be included if a 5% threshold is chosen (5% is the minimum threshold).

- AE reporting is consistent with other document disclosures for example, the CSR, manuscripts, and so forth.

7. References

Wilson EB. Probable inference, the law of succession, and statistical inference. *J Am Stat Assoc.*1927;22:209-212.

Leo Document ID = 870f9863-ede5-4375-8016-4d6980923dfb

Approver: PPD

Approval Date & Time: 04-Mar-2015 03:02:30 GMT

Signature meaning: Approved
